## Appendix F. Youth Tobacco and Nicotine Product Primary Care Questionnaire (YTNP-PCQ)

### TELEPHONE SURVEY QUESTIONNAIRE

**HELLO.** Hello, my name is \_\_\_\_\_ and I'm calling on behalf of the OneFlorida Clinical Research Consortium.

**INTRO.** May I speak with (insert teen's name here)? You enrolled in a teen health study at your doctor's office, and we are calling to ask you a few follow-up questions.

This survey will take approximately 10-15 minutes. Do you want to start now?

*IF NOW IS NOT A GOOD TIME, schedule a time to call back that is convenient for the interviewee.*

*IF NOW IS A GOOD TIME, go to INTRO2.*

**INTRO2.** Before we begin, I need to tell you a few things.

- You do not have to participate in this survey if you don't want to. Refusal will NOT affect your relationship with your pediatrician/healthcare provider.
- I am going to ask you some specific questions about yourself, including questions about your health and the health care provided by your doctors. You can stop this interview at any time. You can skip any question you don't want to answer.

### INTRO3

- All your answers are confidential. We will not report your name or individual responses to your pediatrician/healthcare provider.
- I do not work for your doctor's office. Your doctor's office is part of the OneFlorida Clinical Research Consortium. This is a group of clinics that work together to conduct research in clinical settings. I work for a Survey Research Center and I have been asked by the University of Florida to call study participants to ask about their opinions and experiences. If you have any questions about the study, please contact [name] at [contact]. If you have any questions about your health care, please contact your provider's office.

**1. During this last visit** that you had with a doctor or other health provider, did you complete a checklist or survey about your use of cigarettes and/or other nicotine products (for example e-cigarettes, hookah and snuff)?

- 1  Yes  
 2  No  
 12  Don't Know  
 13  Refused

**2. During this last visit**, did you get a chance to speak with a doctor or other health provider privately? (Meaning one on one - without your parents or other people in the room).

- 1  Yes  
 2  No  
 12  Don't Know  
 13  Refused

**3. During this last visit**, did a doctor or other health provider tell you that what you talked about with them was confidential? (Meaning it would not be shared with anyone else).

- 1  Yes  
 2  No  
 12  Don't Know  
 13  Refused

**4. During this last visit**, did a doctor or other health provider talk with you about any of the following?

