#### 4. Background:

Cigarette smoking remains the most preventable cause of death in the US and contributes significantly to the occurrence of chronic conditions. *Adolescents are a particularly vulnerable and important group to target for tobacco cessation.* Progression from occasional to daily smoking almost always occurs by age 26, an event that substantially increases the risk for chronic disease in adulthood. Moreover, there has been rapid growth in electronic or e-cigarette use and other non-cigarette tobacco products among youth, which may further increase their risk for transitioning to cigarette use and the development of other addictions.

*Primary Care Providers (PCPs) play a critical role in tobacco-related disease screening, counseling, and early intervention among youth.* There is an evidence base demonstrating that PCP brief interventions contribute to overall tobacco cessation and reduction. Yet there are significant gaps in screening and management of risk factors, counseling about e-cigarettes, parental counseling, and follow-up interventions to reduce tobacco and e-cigarette use in primary care.

We are proposing a pilot study to increase PCP capacity to follow evidence-based guidelines for tobacco and nicotine product screening and intervention among youth ages 11 through 17. We selected the 6As intervention for two primary reasons. First, the American Academy of Pediatrics (AAP) and the U.S. Preventive Services Task Force recommend their use. Second, the 6As strategy has an evidence base demonstrating that physician screening, advice, and referrals are effective in contributing to tobacco cessation among adolescents. The 6As are: (1) “Anticipate” (future use), (2) “Ask” (about tobacco use), (3) “Advise” (advise the patient to quit using tobacco), (4) “Assess” (the patient’s readiness to quit using tobacco), (5) “Assist” (by setting a quit date, providing materials on quitting tobacco, providing tobacco cessation medications, and referring the patient for additional services and/or counseling), and (6) “Arrange” (by re-contacting the patient after their quit date and arranging a follow-up visit). Consistent with AAP recommendations, we will include screening for e-cigarette, cigars, chewing tobacco, and hookah use.

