For the medical record review for the UF sites (Gainesville and Jacksonville), certified medical record coders will access Epic, the electronic health record, directly if permission is granted from UF Health to do so. If permission is not granted, the clinic staff will be asked to provide PDFs of the children's records for the selected date ranges for the medical record reviewers to review onsite in the clinics. The 6As and Best Practices Medical Record Review Form (6As MRR - Appendix E) will be stored in UF REDCap.

F. Youth Tobacco and Nicotine Product Primary Care Questionnaire (YTNP-PCQ) (Appendix F): At 30 days post primary care visit, children with parental consent and their assent will be contacted via telephone to complete a 10 minute survey about their recollection of the tobacco and nicotine product discussions held with the clinician during the primary care visit. The YTNP-PCQ is adapted from the questionnaire used in the Adolescent Health Risk Assessment in Primary Care Study.

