Congruence between documentation of the intervention in the EHR and adolescent report of the intervention: Within 30 days post primary care visit, patients will be contacted via telephone to complete the Tobacco and Nicotine Product Primary Care Questionnaire (TNP-PCQ) (Appendix E), which asks about their recollection of the tobacco and nicotine product discussions with their providers during the primary care visit. For each outcome in the TNP-PCQ survey, we will perform a concordance analysis to evaluate the agreement between the medical record review data and patient-reported data. Concordance will be evaluated using the following statistics: sensitivity, specificity, positive predictive value (PPV), negative predictive value (NPV) and the Kappa statistic. Differences in concordance will be tested with the Pearson chi-square test.

**7. Possible Discomforts and Risks.** There are no known risks associated with this study. The only discomfort that the patient may experience may be associated with discussing something that is personal. Patients will be reminded that they can skip any question on the survey questionnaire that they wish. Patients will be informed that they can choose not to participate in in any portion of the discussion and that answering questions is completely voluntary. There is minimal risk in working with personal health information. However, all data will be in a secure database with access limited to a programmer and the study members conducting data analysis. The medical records will be reviewed onsite and will not leave the practice setting or will be reviewed through a secure computer access if permission is granted for UF Health sites.

**8. Possible Benefits.** There are no potential benefits to patient participation.

**9. Conflict of Interest.** None.

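### The telephone items ask about the youth's last visit without naming the study visit, and the call timing is stated two ways, so Aim 3 can compare the chart with recall of a different visit

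*Combined protocol and SAP*

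**What the plan says.** Section 6.2.5 (Analysis Plan, congruence paragraph) defines the youth side of the Aim 3 comparison as "recollection of the tobacco and nicotine product discussions with their providers during the primary care visit". This is set against the medical record review using sensitivity, specificity, PPV, NPV and kappa. Section 6.2.3, item F, has the same target: recall of the discussion at the primary care visit from which the call is timed.

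The instrument is worded differently. Item 1 of Appendix F asks about the last visit "that you had with a doctor or other health provider, did you complete a checklist or survey". Item 2 asks, about the same last visit, "did you get a chance to speak with a doctor or other health provider privately". Items 3, 4, 6, 8 and 9 use the same lead-in. None gives a date, practice or clinician, and none asks about visits since. The only link to the study is in the introduction: "You enrolled in a teen health study at your doctor's office, and we are calling to ask you a few follow-up questions".

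On timing, section 6.2.3 says "At 30 days post primary care visit, children with parental consent and their assent will be contacted via telephone", whereas section 6.2.5 says "Within 30 days post primary care visit, patients will be contacted via telephone".

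On the chart side, section 6.2.3, item E, requests the records of participating patients at the end of the intervention period. It does not say that abstraction is limited to the visit at which the youth was screened.

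**The concern.** A concordance analysis assumes that both sources describe the same encounter. Here neither source is tied to it. A youth who has since been seen elsewhere, or again at the same practice, and who takes the question literally will describe the later visit. That answer is then scored against the chart of the study visit, and a disagreement looks like poor charting or poor recall when it is neither.

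The interval between visit and call matters for the same reason. Both forgetting and the chance of an intervening visit grow with it. Under one section the call comes at about day 30; under the other it may come at any time up to day 30. The script also allows call-backs at a convenient time, with no closing day.

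The data as planned would not show how often this happened, so later analysis could not correct for it.

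**Working it through.** **Which items can be affected.** Setting Appendix F beside the record review form in Appendix E:

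- Item 4 (products discussed) corresponds to Appendix E items 1 and 5.
- Item 6 (talk about quitting) corresponds to Appendix E items 6, 7 and 9.
- Item 8 (household use asked about) corresponds to Appendix E items 10 and 11.
- Item 9 (parent or family member quitting) corresponds to Appendix E items 12 and 13.
- Items 1, 2, 3, 5 and 7 (checklist, privacy, confidentiality, helpfulness) have no chart counterpart.

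**Size.** The plan gives no expected kappa, no sample size for Aim 3 and no rate of intervening visits, so there is no figure to reproduce. All inputs below are assumptions.

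- p = share of study-visit charts that document the discussion
- m = share of youths who answer about another visit
- r = chance that the other visit included the discussion, taken as independent of the study-visit chart
- Se, Sp = sensitivity and specificity of youth report, with the chart as reference, when the visits match

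Observed sensitivity S = (1 − m)·Se + m·r. Observed specificity T = (1 − m)·Sp + m·(1 − r). Kappa = (po − pe)/(1 − pe), where po = p·S + (1 − p)·T. The youth-yes share is y = p·S + (1 − p)(1 − T), and pe = p·y + (1 − p)(1 − y).

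*Perfect charting and recall* (Se = Sp = 1, p = 0.80, r = 0.20). At m = 0.10:

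- S = 0.90 + 0.02 = 0.92 and T = 0.90 + 0.08 = 0.98
- po = 0.736 + 0.196 = 0.932
- y = 0.736 + 0.004 = 0.740
- pe = 0.592 + 0.052 = 0.644
- kappa = 0.288/0.356 = 0.809
- PPV = 0.736/0.740 = 99.5%

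| m | Maximum sensitivity | PPV | Maximum kappa |
|---|---|---|---|
| 5% | 96% | 99.7% | 0.899 |
| 10% | 92% | 99.5% | 0.809 |
| 20% | 84% | 98.8% | 0.653 |

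*Imperfect recall* (Se = Sp = 0.90). Kappa at each m:

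| p | r | 0% | 5% | 10% | 20% | 30% |
|---|---|---|---|---|---|---|
| 0.50 | 0.10 or 0.50 | 0.80 | 0.76 | 0.72 | 0.64 | 0.56 |
| 0.80 | 0.10 | 0.72 | 0.65 | 0.58 | 0.47 | 0.38 |
| 0.80 | 0.50 | 0.72 | 0.67 | 0.62 | 0.53 | 0.45 |

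The direction is the same throughout. The loss depends on m, and at m = 0 there is none.

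**The case against.** The script is not wholly unanchored. The caller opens by saying "You enrolled in a teen health study at your doctor's office", and item 1 cues the study event by asking about a nicotine checklist. For a youth with no later visit, the last visit is the study visit. This stands: mismatch is possible, not certain. But the introduction never ties the last visit to enrolment. Item 1 cannot act as a filter, because it has no routing and a negative answer may mean either a different visit or forgetting.

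A reader might infer that the error falls mainly on tobacco users, because the Arrange step of the 6As works "by re-contacting the patient after their quit date and arranging a follow-up visit" and so creates later visits. The documents do not support that. Nothing places the Arrange contact before the call. Users are expected to be about 9% to 11% of those screened (20/218 = 9.2% on the figures in section 6.2.2; 20/190 = 10.5% with the number in section 6.2.3), and only those wanting to quit would have a quit date. A cessation follow-up would also probably include the tobacco discussion. With r = 1 and perfect recall, S = (1 − m) + m = 100%, so no sensitivity is lost for them. The calculation above uses a single m and r whatever the chart shows, so it gives no evidence of differential error.

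A reader might also infer that every telephone item and every statistic suffers. Only four items have a chart counterpart, and in the perfect-recall illustration PPV stays at 98.8% or above.

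Finally, this is a pilot, and its primary outcome is taken from the chart and is untouched. That limits the weight of the point but does not remove it, since congruence is one of three stated aims.

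**Conclusion.** Two textual facts are firm. The telephone items do not identify the visit that Aim 3 needs, and the two sections disagree on when the call is made. In addition, the chart abstraction is not stated to be limited to that visit. A mismatch of visits can therefore lower agreement on items 4, 6, 8 and 9 without being detectable afterwards.

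The size is unknown. The figures in the working rest wholly on assumed prevalence, assumed content of the other visit and an assumed share of youths affected; they show sensitivity to the problem and are not forecasts. It would go too far to conclude that Aim 3 cannot be answered: if few youths are seen again before the call, the effect is negligible. The point is worth acting on because the correction is cheap and must be made before data are collected.

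**What to change.** - **Script.** Before item 1, have the interviewer read out the date of the study visit and the practice name, and refer to that visit in every item. The study should already hold both, since the call is timed from the visit.
- **Later visits.** Add one item asking whether the youth has seen a doctor or other provider since that date. Plan a sensitivity analysis of the concordance statistics that excludes those who have.
- **Chart side.** State in section 6.2.3, item E, or section 6.2.5 that the Aim 3 abstraction is restricted to the same dated visit. Without this, correcting the script alone leaves the two sources free to differ.
- **Timing.** State one call window, with a closing day, in both section 6.2.3 and section 6.2.5, and record the interval from visit to call.

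The cost is one extra question, a slightly longer script and a few aligned sentences. No additional patients or staff are needed.

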**A. Chewing tobacco or snuff**

- 1  Yes  
 2  No  
 12  Don't Know  
 13  Refused

**B. Smoking cigarettes?**

- 1  Yes →.  
 2  No →  
 12  Don't Know →  
 13  Refused →

**C. Using e-cigarettes?**

- 1  Yes →.  
 2  No →  
 12  Don't Know →  
 13  Refused →

**D. Smoking hookah?**

- 1  Yes →.  
 2  No →  
 12  Don't Know →  
 13  Refused →

5. How helpful was this discussion in understanding the risks of cigarettes or using any nicotine products such as e-cigarettes to your health?

- 1  Not at all helpful  
 2  Somewhat helpful  
 3  Helpful  
 4  Very helpful  
 5  Not sure  
 13  Refused

6. **During this last visit**, did you and a doctor or other health provider talk about how and why to quit smoking or using nicotine products (such as setting a date to quit)?

- 1  No because I do not smoke or use nicotine products  
 2  Yes → **If YES go to 7.**  
 2  No → **If NO go to 8.**  
 3  No, because I did not tell my doctor or other health provider that I smoke cigarettes or use nicotine products → **If NO go to 8.**  
 12  Don't Know → **If DON'T KNOW go to 8.**  
 13  Refused → **If REFUSED go to 8.**

7. How helpful were your discussions in quitting smoking or using nicotine products?

- 1  Not at all helpful  
 2  Somewhat helpful  
 3  Helpful  
 4  Very helpful  
 5  Not sure

8. **During this last visit**, did a doctor or other health provider ask you if your parents or anyone else living with you smoked cigarettes or used nicotine products?

- 1  Yes. **Go to 9**  
 2  No. **Go to** closing thank you  
 12  Don't Know **Go to** closing thank you  
 13  Refused **Go to** closing thank you

9. **During this last visit**, did a doctor or other health provider talk to you a parent or family member about quitting smoking or using nicotine products?

- 1  No because no one living with me smokes cigarettes or uses tobacco products  
 2  Yes **Go to** closing thank you  
 3  No **Go to** closing thank you  
 4  No because my parent/family member did not tell the doctor (or health care provider) they smoke or use nicotine products **Go to** closing thank you  
 12  Don't Know **Go to** closing thank you  
 13  Refused **Go to** closing thank you

**Those are all of the questions we have. In order to receive your \$5.00 Amazon electronic gift card, we need to verify that we have your correct address and email address.**

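### Appendix F, question 6 prints one code for both Yes and No, so answers keyed as printed do not by themselves give the split that the Aim 3 concordance statistics need

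*Combined protocol and SAP*

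**What the plan says.** Appendix F, Q6, is the telephone item on the youth's own quit discussion. It asks whether youth and provider did "talk about how and why to quit smoking or using nicotine products (such as setting a date to quit". The printed answers are:

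- code 1, "No because I do not smoke or use nicotine products", with no routing instruction;
- code 2, "Yes → If YES go to 7";
- code 2 again, a plain No, routed to Q8;
- code 3, "No, because I did not tell my doctor or other health provider that I smoke cigarettes or use nicotine products", routed to Q8;
- codes 12 and 13, Don't Know and Refused, both routed to Q8.

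Q7 then asks "How helpful were your discussions in quitting smoking or using nicotine products" and offers codes 1 to 5, the last being Not sure. It has neither a Refused nor a not-applicable option. The interviewer's introduction tells the youth: "You can skip any question you don't want to answer".

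Section 6.2.5 sets out the use of these answers: "For each outcome in the TNP-PCQ survey, we will perform a concordance analysis to evaluate the agreement between the medical record review data and patient-reported" information. The listed measures are "sensitivity, specificity, positive predictive value (PPV), negative predictive value (NPV) and the Kappa statistic".

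**The concern.** Two opposite answers to Q6 share one stored value. Every measure listed in section 6.2.5 is built from a two-by-two table of chart against youth report, and such a table needs each youth placed in Yes or No. A data file that holds only the printed Q6 code cannot do this for anyone coded 2.

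The item matters within Aim 3 because it is the only telephone question on the youth's own quit discussion. It is the nearest youth-reported counterpart to advice to quit, one of the measures named in section 6.2.5, and to the chart items in Appendix E on readiness to quit, referral and quit resources. Section 6.2.2 aims for only 20 users per practice, so a few unclassifiable answers among users would be noticeable.

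The second defect is distinct. The non-user answer is the only one in Q6 without a route. Read in order, the next item is Q7, so non-users would be asked to rate a quit discussion that they have just said did not take place.

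**Working it through.** The plan states no figure on this point, so the check sets the printed codes and routes beside the planned use.

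**1. Codes and routes in Q6 (Appendix F)**

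| Answer (paraphrased) | Code | Printed route | Next item |
|---|---|---|---|
| No, non-user | 1 | none | Q7 by default |
| Yes | 2 | Q7 | Q7 |
| No | 2 | Q8 | Q8 |
| No, use not disclosed | 3 | Q8 | Q8 |
| Don't know | 12 | Q8 | Q8 |
| Refused | 13 | Q8 | Q8 |

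There are six answers and five distinct codes, and five answers with a route and one without.

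**2. Does the rest of the instrument settle what 2 means?** No. In Q4 and Q8, 2 is No. In Q9, which has the same type of answers as Q6, 2 is Yes, and the codes there are all distinct (1, 2, 3, 4, 12, 13). No codebook appears in the documents.

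**3. How much can routing recover?** Let Y be the number answering Yes, N the number answering plain No, and k the number of Yes respondents who leave Q7 blank. If interviewers follow the routes:

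- code 2 with Q7 answered: Y − k, all Yes;
- code 2 with Q7 blank: N + k, a mixture.

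Counting every blank as No misclassifies k youths. If k = 0, recovery is complete. The documents give no basis for k. It can exceed zero because any item may be skipped, and Q7 has no Refused code that would mark such a case as having reached Q7.

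**4. Does the missing skip affect Q6?** No. Non-users keep code 1, which no other answer shares. It affects Q7, and dropping records with Q6 = 1 removes the effect.

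**5. How many respondents could take the default path to Q7?** This has to be assumed, because the documents give neither a telephone response rate nor the prevalence of any-product use at ages 11 to 17. Three figures in section 6.2.2 give a range:

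- 11% (e-cigarettes, Florida high school students, 2014): 1 − 0.11 = 0.89 non-users;
- 20/218 = 9.2% (implied by the screening target): 1 − 0.092 = 0.908;
- 4.3% (cigarettes, ages 11 to 17): 1 − 0.043 = 0.957.

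With the approximately 190 youths per intervention practice in section 6.2.3, these give 0.89 × 190 = 169, 0.908 × 190 = 173 and 0.957 × 190 = 182. Each count also assumes that every screened youth is reached and that every non-user chooses answer 1 rather than plain No. They are illustrations, not estimates. Use of any product could be higher than the single-product figures, but non-users remain the majority as long as fewer than half of respondents use any product.

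**The case against.** The strongest reply is that this is a numbering slip in a printed script. The Yes and No labels and their routes are distinct, so an interviewer would not be confused. Calls are made through a survey research centre (section 6.2.2), and whether the printed numbers became stored codes is unknown. A slip in reading the PDF cannot be excluded either, although the sequence 1, 2, 2, 3 looks like an error in the source. This reply stands, and it keeps the point small. It does not remove the point, because nothing in the documents corrects the codes.

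Four stronger readings are tempting, and the documents do not support them:

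- A reader might infer that the missing skip also makes Q6 ambiguous. It does not, since non-users have their own code.
- A reader might infer that the Yes/No answer is lost altogether. The different routes for Yes and No recover most of it.
- A reader might infer that Q6 is the only telephone item on quit counselling. Q9 asks about quitting talks with a parent or family member, and Appendix E has a matching chart item on advising parents to quit. Q6 is alone only for the youth's own discussion.
- A reader might infer that the Q7 problem damages a planned result. Section 6.2.5 names no helpfulness analysis, and the chart form has no counterpart to Q7.

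It is also fair to say that Q7's Not sure option does the work of a Don't Know code, as in Q5. Only Refused is missing; Q5 has it.

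**Conclusion.** The instrument is wrong as printed. Keyed that way, Q6 alone cannot supply the youth-report side of the concordance table for the youth's own quit discussion, and Q7 completion repairs this only in part. The residual error is the number of Yes respondents with a blank Q7, which the documents do not allow one to estimate. The unrouted non-user answer is a separate nuisance, confined to Q7 and removable.

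Severity is minor. One item of a secondary aim in a pilot is affected, and the primary outcome is taken from medical records (section 6.2.5). The conclusion assumes that the printed codes are the stored codes and that no corrected field version exists. If the programmed survey stores Yes and No separately, the Q6 coding problem disappears.

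**What to change.** In Appendix F, before calls begin:

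1. Give each Q6 answer its own code, for example 1 to 4, 12 and 13, as Q9 already does.
2. Route the non-user answer to Q8.
3. Add Refused (13) to Q7.

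In section 6.2.5, state how the non-user answer and the undisclosed-use answer enter the concordance table: as No, or as not applicable and excluded. Renumbering alone does not settle this.

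The cost is a short questionnaire edit, one sentence in the analysis plan, and a check that the survey centre's program matches. If calls have already been made, first check the stored codes. If Yes and No do share a value, classify code 2 with Q7 answered as Yes, and report the concordance measures twice, with code 2 and Q7 blank taken once as No and once as Yes, so that the reader sees the range.

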### 6.2.2 Sample

In Florida, only 4.3 percent of children ages 11 to 17 are current cigarette smokers. However, e-cigarette use is increasing from 5 percent of Florida high school students in 2013 to 11 percent in 2014. While the percentage of adolescents at risk to begin smoking is not known, studies have identified maternal smoking, trying tobacco, alcohol or marijuana by 8th grade, and endorsement of sensation seeking behavior as risk factors for tobacco and related product use. Children should be screened for these risks.

We will screen all youth, ages 11 through 17 years, in the practice for current tobacco use and risk behaviors associated with cigarette and nicotine product use with the goal of reaching 20 children per practice who are current tobacco users who could receive at least one or more of Steps 3 through 6 (advise, assess, assist, arrange). To achieve 20 patients per practice who reach the “advise” and “assess” stages, if the practice had the average percentage of children using e-cigarettes, approximately 218 patients would need to be screened. The number screened to reach the “advise” and “assess” stages is based on the e-cigarette use and not the traditional cigarette use.

Intervention practices will be asked to screen patients for tobacco and nicotine product use (using the anticipate and ask components of the 6As) by having youth complete a tobacco and nicotine use screening tool until the practice has identified and completed at least the “advise” and “assess” intervention on 20 tobacco/nicotine users. Parental consent and adolescent assent will be electronically obtained using ResearchActs software. In addition, practices will be asked to implement a short parental screening tool for tobacco use. The parent and child will respond to the surveys separately. After the child completes the survey s/he will be offered a \$5 electronic Amazon gift card.

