The duration of the study participation for patients is variable. For those who do not smoke/use nicotine products or who smoke/use nicotine products but do not want to quit, the duration of the study is the baseline data collection (5 to 10 minutes for the youth and 5 to 10 minutes for the parent, inclusive of the informed consent), clinician screening and advising (2 to 5 minutes for the child and 2 to 5 minutes for the parent), and the follow-up telephone survey administered through the UF Survey Research Center (10 minutes) for a total estimated participation time of approximately 25 to 30 minutes. Adolescent participants will be offered another \$5 electronic Amazon gift card after completion of the follow-up telephone survey. For patients who smoke/use nicotine products and want to quit, their participation is an estimated 35 minutes for baseline and follow-up telephone survey data collection and provider discussion during the primary care visit. Practices can customize who conducts the screening and advising. For example, some practices assign that role to the nursing staff. In other practices, the clinician seeing the patient for the visit provides this screening and counseling himself or herself.

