**Best Practice:**

1. Documentation that youth was asked about current use of:
  - a. Cigarettes
  - b. Cigars/Cigarillos
  - c. E-cigarettes
  - d. Hookah
  - e. Smokeless tobacco products
2. If youth smokes or uses nicotine products, was youth asked about amount used (e.g., just a puff, 5 cigarettes a day and so on)?
3. If youth smokes or uses nicotine products, was youth asked about how often used (e.g., daily, monthly and so on)?
4. Was youth asked if he/she anticipated using cigarettes or nicotine products in the future?
5. Was youth advised to not use: Cigarettes, Cigars/cigarillos, E-cigarettes, Hookah, or Smokeless tobacco products
6. For those who smoke or use tobacco products was youth asked if they were ready to quit?
7. For those who were ready to quit, was a referral made?
8. Regardless of readiness to quit, were youth given or told about resources that are available to learn more about the hazards of tobacco and nicotine use?
9. Regardless of readiness to quit, was youth given/told about resources to quit should s/he decide to do so?
10. Was parental tobacco use assessed?
11. Were parent(s) asked about?
  - a. Smoke free home
  - b. smoke free car
  - c. If anyone caring for the child smokes
12. If parent(s) smokes or uses nicotine products in the home or car, was s/he advised to quit smoking?
13. If parent(s) smokes, was s/he referred to smoking cessation programs?
14. If parent(s) smokes was s/he told about educational resources on the influence of parental smoking on the child/youth?

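### Telephone question 9 on parent quit advice is skipped unless the youth reports being asked about household use, so the youth report of that advice is selectively missing for Aim 3

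*Combined protocol and SAP*

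**What the plan says.** **Telephone survey (Appendix F).** Question 8 asks the youth whether "did a doctor or other health provider ask you if your parents or anyone else living with you smoked cigarettes or used nicotine products". Yes goes to question 9. The next line reads "No. Go to closing thank you", and Don't Know and Refused are routed the same way. Question 9 then asks "did a doctor or other health provider talk to you a parent or family member about quitting smoking or using nicotine products". It is the last substantive item and the only one on this event. One of its answer options is "No because my parent/family member did not tell the doctor (or health care provider) they smoke or use nicotine products".

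**Parent screening in the intervention (Section 6.2.2).** The plan states that "practices will be asked to implement a short parental screening tool for tobacco use" and that "The parent and child will respond to the surveys separately". The time estimate for a visit includes "clinician screening and advising (2 to 5 minutes for the child and 2 to 5 minutes for the parent". Section 6.2.3, item D, describes the parent questionnaire.

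**Record review (Appendix E).** Item 12 reads "If parent(s) smokes or uses nicotine products in the home or car, was s/he advised to quit smoking". It is conditional on a parent's use, but not on the youth having been asked anything.

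**Analysis (Section 6.2.5).** For each outcome in the telephone survey, agreement with the medical record is to be described by sensitivity, specificity, positive and negative predictive value, and Kappa. Nothing is said about items left unasked by routing.

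**The concern.** The filter and the item behind it concern different events. Question 8 is about a provider asking the youth. Question 9 is about a provider talking with a parent. The plan itself treats these as separate acts: the Clinician Survey (Appendix A) has one item for asking the patient about household use (5e) and another for asking the accompanying parent (5f). The last-quoted answer option of question 9 also presupposes an exchange between parent and provider, which question 8 does not detect.

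A parent can therefore be screened on the parent questionnaire, advised by the clinician and charted as advised, while the youth truthfully answers No to question 8. The interview then ends. At stake is the Aim 3 result for parent quit advice: the youth's answer is missing for a reason tied to how the visit was conducted, and it cannot be recovered once the calls are over.

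**Working it through.** The plan gives no figure for this point, so there is none to reproduce. The check is a routing trace followed by a bound.

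**Routing trace**, from Appendix F questions 8 and 9:

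| Who was asked about household use | Youth's answer to question 8 | Question 9 |
|---|---|---|
| Parent directly, and youth reports being asked | Yes | Asked |
| Parent directly, and youth does not report being asked | No, Don't Know or Refused | Skipped, even if the parent was advised to quit |
| Youth only | Yes | Asked |
| Neither | No | Skipped |

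The loss that matters is in the second row. It covers some of the directly screened families, not all of them.

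**Effect on agreement.** Section 6.2.5 does not name the pairs to be compared. I take Appendix E item 12 as the natural partner of question 9, because both concern advising a parent to quit. Among interviewed families with parent quit advice in the chart, let *s* be the share whose youth answers Yes to question 8, and *r* the share of those who then answer Yes to question 9.

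- *Skips coded No:* sensitivity = *s* × *r*. Since *r* cannot exceed 1, sensitivity cannot exceed *s*, even with perfect recall.
- *Skips dropped:* the estimate is *r* alone, from youths who recall being asked. It says nothing about the remaining share, 1 − *s*.

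The documents give no value for *s*. For illustration, per 100 interviewed families with charted parent advice:

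| Assumed *s* | Question 9 asked | Question 9 skipped | Highest possible sensitivity, skips coded No |
|---|---|---|---|
| 25% | 25 | 75 | 25% |
| 50% | 50 | 50 | 50% |
| 75% | 75 | 25 | 75% |

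**Denominator.** The bound uses charted-advice families only, and item 12 applies to all of these. Specificity, negative predictive value and Kappa also use families without charted advice. Appendix E offers only Yes or No, so in a pool of all interviewed youths those three statistics would depend on how reviewers coded item 12 where no parent uses tobacco or nicotine.

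**Is the filter needed?** Question 9 already has codes for a home with no user, for a parent who did not disclose use, and for Don't Know. Every respondent could be asked it without a new answer option.

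**The case against.** The strongest counter-argument is that direct parent screening does not stop the youth from being asked as well. The intervention youth questionnaire (Appendix C) has an item on who at home uses tobacco, and under Section 6.2.3, item C, the clinician reviews the youth's answers at the visit with prompts for the 6As. That stands, and it limits the point. A reader might infer that question 9 is never put to families whose parent was screened directly; the documents do not support that. They also do not show that the route is closed off by design, or that every youth would count a tablet item as being asked by a provider.

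A reader might also infer that the loss grows as the parent questionnaire works better. Nothing in the plan settles the direction: a clinician alerted by either questionnaire may raise household use with both parent and youth, which would produce more Yes answers to question 8. Nor can one state how far sensitivity would fall in practice. That would need a recall rate, a skip rate specific to advised families and a coding rule for skips, and the plan gives none of these.

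The scope is narrow. Question 8 and the earlier items are asked before the skip and are unaffected. The garbled wording of question 9 looks like a dropped word and would be editorial on its own. It still needs repair, because the item can be read as a talk with the youth about a parent or as a talk with the parent, and only the second matches item 12.

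**Conclusion.** The point holds in a limited form. Question 9 is skipped whenever the youth does not answer Yes to question 8, and this includes some families whose parent was screened and advised directly, as the intervention provides. The youth report of parent quit advice is therefore selectively missing for Aim 3, and neither obvious treatment of the skips repairs it. The size is unknown. What can be stated without a recall assumption is the ceiling: with skips coded No, sensitivity cannot exceed the share of charted-advice families whose youth answers Yes to question 8. The conclusion assumes that the printed routing is followed in the calls and that question 9 is compared with item 12.

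A reader might infer that the main result is at risk. It is not: Section 6.2.5 takes the primary outcome, including discussion of the parent's tobacco use, from the medical records. The change is worth making because it protects a stated aim at almost no cost.

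**What to change.** 1. In Appendix F, route every answer to question 8 on to question 9.
2. Reword question 9 to one event: whether a provider talked with a parent or other family member about quitting. Keep the existing answer options.
3. In Section 6.2.5, name Appendix E item 12 as its comparator and restrict the agreement tables to families to whom item 12 applies, that is, a parent who uses tobacco or nicotine. This can be taken from the chart or, in intervention practices, from the parent questionnaire. If agreement is compared between groups, define applicability from the same source in both.
4. State how Don't Know answers enter the tables, for example as a separate category with a sensitivity analysis counting them as No.

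The cost is one skip edit, one wording edit, a few sentences in the analysis plan and a few seconds per call.
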